11.7 Assessment of Severity

The severity of clinical AEs will be assessed according to the scale in Tables 6-7:

Table 6. Severity grading criteria for physical observations.

	Grade 1 (mild)	Grade 2 (moderate)	Grade 3 (severe)
Fever (oral)	37.6°C - 38.0°C	38.1°C – 39.0°C	>39.0°C
Tachycardia (bpm)*	101 - 115	116 – 130	>130
Bradycardia (bpm)**	50 – 54	40 – 49	<40
Systolic hypertension (mmHg)	141 - 159	160 – 179	≥180
Diastolic hypertension (mmHg)	91 - 99	100 – 109	≥110
Systolic hypotension (mmHg)***	85 - 89	80 – 84	<80

*Taken after ≥10 minutes at rest; **When resting heart rate is between 60 – 100 beats per minute. Use clinical judgement when characterising bradycardia among some healthy volunteer populations, for example, conditioned athletes; ***Only if symptomatic (e.g. dizzy/ light-headed)

Table 7. Severity grading criteria for local and systemic AEs399

GRADE 0	None
GRADE 1	Mild: Transient or mild discomfort (< 48 hours); no medical intervention/therapy required
GRADE 2	Moderate: Mild to moderate limitation in activity – some assistance may be needed; no or minimal medical intervention/therapy required
GRADE 3	Severe: Marked limitation in activity, some assistance usually required; medical intervention/therapy required, hospitalisation possible

11.8 Procedures to be followed in the event of abnormal findings

Eligibility for enrolment in the trial in terms of laboratory findings will be assessed as detailed in Section 9.4. Abnormal clinical findings from medical history, examination or blood tests will be assessed as to their clinical significance throughout the trial. Laboratory adverse events will be assessed using the site-specific tables in the Site Master File/TMF. If a test is deemed clinically significant, it may be repeated, to ensure it is not a single occurrence. If a test remains clinically significant, the volunteer will be informed and appropriate medical care arranged as appropriate and with the permission of the volunteer. Decisions to exclude the volunteer from enrolling in the trial or to withdraw a volunteer from the trial will be at the discretion of the Investigator.

11.9 Local Safety Committee

A Local Safety Committee (LSC) will be appointed to provide real-time safety oversight. The LSC will be notified within 24 hours of the Investigators' being aware of the occurrence of SAEs. The LSC has the power to place the study on hold if deemed necessary following a study intervention-related SAE. At the time of writing the LSC will be chaired by [name], Clinical Tutor in Medicine, Honorary Consultant Physician and Director of the Oxford Centre for Clinical Tropical Medicine at Oxford University. There will be a minimum of two other appropriately qualified committee members. All correspondence between Investigator and LSC will be conveyed by the Investigator to the trial Sponsor. The chair of the LSC will be contacted for advice and independent review by the Investigator or trial Sponsor in the following situations:

- Following any SAE deemed to be possibly, probably, or definitely related to the trial vaccine.
- Any other situation where the Investigator or Trial Sponsor feels independent advice or review is important.

Safety Profile Review

The safety profile will be assessed on an on-going basis by the Investigators. The Chief Investigator, Principal Investigator, and relevant Investigators (as per the trial delegation log) will also review safety issues and SAEs as they arise.

12 STATISTICS

This is primarily a safety trial with descriptive endpoints. Following the first three volunteers enrolled into the starter group, 3-6 volunteers will be recruited into Group A, to receive the target dose. Due to existing difficulties recruiting to this clinical trial we have decided to take out Group B (the comparator arm) to ensure that the numbers recruited will still be sufficient to allow for the primary objective, an assessment of safety. A twofold increase in the magnitude of the cellular immune response (as measured by ELISpot response to 85A peptide stimulation) is considered immunologically

meaningful. This sample size is appropriate for a proof-of-concept Phase I safety study and takes into account the low number of potentially eligible healthy adults with latent *M.tb* infection in the UK and the impact of this on recruitment. The sample size has not been determined with the aim of achieving statistical significance.

It is anticipated that the immunological endpoints will not follow a normal distribution. The one-week and three-month responses will be compared. Medians and interquartile ranges will be used to summarise the data and the Mann Whitney U test will be used for statistical comparisons. An area-under-curve analysis will be used to compare the overall responses over time comparing these aerosol data with historical data from previous trials. This analysis will make use of data collected at all time points.

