6.2 Rationale

Hypothesis

We postulate that the aerosol inhaled route is practical and feasible and has an acceptable safety profile, in volunteers latently infected with *M.tb*. We hypothesise that the aerosol inhaled route of administration will induce greater mucosal immunity and comparable systemic immunity when compared to historical data of the IM (systemic) route of administration from previous studies in healthy volunteers.

Vaccine dosage

Trials of MVA85A to date have established 1×10^8 pfu as the optimal dose for intradermal injection in adults. Although the fractional delivered dose of aerosolised viral vectored vaccines to the mucosal surface may be considerably less than 25%, there is evidence that strong mucosal and systemic immune responses, comparable to the injectable route, are nevertheless achieved (16, 64).

As this trial will be the first time that aerosolised MVA85A is given to individuals with latent *M.tb* infection, we plan to begin with a low dose Starter Group, who will receive 1×10^7 pfu MVA85A by aerosol inhalation. This is the dose used in trial TB026 in healthy adults. The first volunteer in this group will be vaccinated ahead of other volunteers and no other volunteers will be vaccinated until at least 48 hours has elapsed. The CI will perform a review of the 48 hour safety data and decide if it is safe to vaccinate the remaining volunteers. There will be a second review of safety data after vaccination of all volunteers in the Starter Group.

Once the Starter Group is fully enrolled and the second safety review is completed, we will start enrolment into Group A (Standard Dose), with dose escalation to 5×10^7 pfu (the same dose used in TB035). For safety reasons, the first volunteer in this group will be vaccinated ahead of other volunteers and no other volunteers will be vaccinated until at least 48 hours has elapsed. If the CI

decides it is safe to proceed, the remaining volunteers will then be enrolled. The target enrolment for this group is 6 volunteers. However, given the often reduced pace of recruitment from the latently infected population, we will accept a minimum of 3 volunteers if the target has not been reached by October 2018.

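### Section 6.2 hypothesises systemic immunity comparable to historical IM data, but section 12 names only a difference test and plans no interval for the historical contrast, so no planned output can support or refute that claim.

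*Combined protocol and SAP*

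**What the plan says.** The hypothesis in section 6.2 has a mucosal half (greater immunity than by the IM route) and a systemic half: "comparable systemic immunity when compared to historical data of the IM (systemic) route of administration from previous studies in healthy volunteers". Neither section 6.2 nor any other section defines *comparable*.

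Section 12 says the following on analysis:

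- One-week and three-month responses will be compared, without saying what with what. Data are summarised by medians and interquartile ranges, and "the Mann Whitney U test will be used for statistical comparisons".
- The historical comparison comes in the next sentence: "An area-under-curve analysis will be used to compare the overall responses over time comparing these aerosol data with historical data from previous trials". No test, interval or margin is attached to it.
- On effect size, "A twofold increase in the magnitude of the cellular immune response" by ELISpot is called immunologically meaningful. Only an increase is mentioned.
- On numbers, "3-6 volunteers will be recruited into Group A, to receive the target dose". On intent, "This is primarily a safety trial with descriptive endpoints" and "The sample size has not been determined with the aim of achieving statistical significance".

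**The concern.** A hypothesis of similarity needs an estimate of the difference and a statement of how large a difference the data still allow. A test whose null is no difference supplies neither. If it is significant, it argues against similarity. If it is not, the groups may be alike or the sample may be too small to tell, and the second explanation gains weight as Group A shrinks from 6 to 3. If a null result were taken as support, the hypothesis would become easier to confirm the fewer volunteers were recruited.

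The Mann Whitney test is for independent samples. With Group B removed, a one-week versus three-month comparison is within volunteer, so the historical contrast is a natural place for a reader to apply the test. If the test is not meant for that contrast, the systemic hypothesis has no inferential method at all. Either way the gap is the same.

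At stake is how a secondary result is reported. Section 6.1 calls the safety and immunogenicity data from this trial critical to deciding whether the route goes forward in high-burden countries. A real loss of systemic response should not pass as comparable merely because few volunteers were studied.

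**Working it through.** The plan states no power, alpha, SD or margin, so it has no figure to reproduce. The check asks how often a true halving of the systemic response would be non-significant, and how wide an interval would be.

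**Inputs from the documents**

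- Aerosol volunteers at the target dose: n = 3 to 6 (section 12).
- Historical IM volunteers: m = 12 (TB022 IM arm, Table 2), or m = 48 (all IM recipients in completed trials, section 6.1). Table 2 agrees: 12 in TB022 + 18 + 18 in TB036 = 48.

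**Assumptions not in the documents**

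- Two-sided alpha 0.05.
- Log-normal responses with equal SD in both groups.
- Between-volunteer SD of the log10 response 0.3 to 0.5, with 0.2 as a favourable case.
- True aerosol/historical ratio 0.5, a shift of log10(0.5) = -0.301. This is the mirror image of a twofold increase, not a figure the plan uses.

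**Step 1: the test.** An exact two-sided Mann Whitney test against 12 historical volunteers rejects when the smaller U is at most 4 of 36 (n=3) or at most 14 of 72 (n=6). Simulation gives the share of trials in which a true halving is non-significant:

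| Historical m | log10 SD | n=3 | n=6 |
|---|---|---|---|
| 12 | 0.2 | 47% | 25% |
| 12 | 0.3 | 73% | 58-60% |
| 12 | 0.4 | 81-82% | 75% |
| 12 | 0.5 | 87% | 82% |
| 48 | 0.3 | 65-66% | 42% |
| 48 | 0.4 | 77-78% | 64% |
| 48 | 0.5 | 84-85% | 75% |

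Ranges within a cell are differences between simulation runs. On the natural-log scale, log10 SD 0.3 is 0.3 × 2.303 = 0.69. Against 12 volunteers, the halving is missed more than half the time once the natural-log SD exceeds about 0.48 at n=3 or 0.62 at n=6 (log10 SD about 0.21 and 0.27). Against 48 the thresholds are about 0.56 and 0.78 (log10 about 0.24 and 0.34).

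**Step 2: the interval.** On the log10 scale the half-width of a 90% interval is t(0.95, n+m-2) × SD × √(1/n + 1/m). With SD 0.3 and m = 12:

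- n=3: 1.771 × 0.3 × √(1/3 + 1/12) = 1.771 × 0.3 × 0.645 = 0.343, and 10^0.343 = 2.20-fold either way.
- n=6: 1.746 × 0.3 × √(1/6 + 1/12) = 1.746 × 0.3 × 0.5 = 0.262, and 10^0.262 = 1.83-fold either way.

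**Step 3: a formal equivalence rule.** Suppose comparability required the whole 90% interval to lie within 0.5 to 2.0. With a true ratio of 1, SD 0.3 and m = 12, the rule would be met in about 5% of trials at n=3 and 24% at n=6. At SD 0.4 or more it would be met in at most about 9%, even with n=6 and m=48.

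**The case against.** A reader might infer that the sponsor intends to read a non-significant Mann Whitney result as comparability. The documents do not say so. Section 12 calls the endpoints descriptive and discloses that the sample size was not chosen for significance. The secondary objective (Table 3) is to evaluate immunogenicity, not to compare routes, and *comparable* enters only through the hypothesis in section 6.2. The Mann Whitney sentence follows the one-week and three-month comparison, so its use for the historical AUC contrast is one reading. This all stands and limits the point to an omission. Medians, interquartile ranges and AUCs can be set beside historical values, but without an interval they do not show what difference the data still allow.

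A reader might also conclude that a halving would usually be missed. That depends on an SD the documents do not give. At log10 SD 0.2 it is more often detected than missed, even at n=3, and with 48 historical volunteers and n=6 it is more often detected at SD 0.3. Pooling the three Starter volunteers, which the plan neither states nor excludes, would give n = 6 to 9. At n=9 against 12, a natural-log SD of 0.7 gives 54% power, so 46% missed.

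Finally, section 12 does not supply an equivalence margin. It calls only a twofold increase meaningful, so a 0.5 to 2.0 range would be a new choice, and Step 3 shows it would seldom be met. Nor does section 6.1 tie a go/no-go decision to systemic comparability; its stated imperative is safety.

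**Conclusion.** The point holds as a mismatch between hypothesis and analysis, which needs no numerical assumption: a similarity claim, only a difference test named, no interval for the historical contrast and no meaning given to *comparable*.

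The figures show that a null result would be weak evidence. For a true halving against 12 historical volunteers, it would occur in about 73-87% of trials at n=3 and 58-82% at n=6 (log10 SD 0.3 to 0.5, two-sided 0.05, log-normal data). At SD 0.2 this falls to about 47% and 25%; with 48 historical volunteers at SD 0.3, to about 66% and 42%. A null result could often, not always, be mistaken for comparability. The documents support neither the claim that it will be read that way nor the claim that it would usually mislead whatever the SD.

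This is a worthwhile, inexpensive correction to a secondary analysis. It does not affect the primary safety objective.

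**What to change.** In section 12, for the aerosol-versus-historical systemic comparison:

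1. Report the aerosol/historical ratio of ELISpot AUC (ratio of geometric means, or Hodges-Lehmann ratio on the log scale) with a confidence interval at a level stated in advance.
2. State that this comparison is descriptive.
3. State that a non-significant difference test will not be taken as evidence of comparability.
4. Read the interval against a twofold difference in either direction as a reference only. A formal 0.5 to 2.0 rule is optional and would need the sponsor's own justification.

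The Mann Whitney test may stay for the directional mucosal claim.

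The cost is a sentence or two and one interval, with no extra volunteers, samples or visits. The drawback is that with 3-6 volunteers the interval will be wide (Step 2), so the result will often have to be reported as inconclusive.

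The report should also carry a caveat. The historical IM groups in Table 2 received 1 × 10⁸ pfu and were BCG-vaccinated UK adults (TB022) or Ugandan adolescents (TB036). Group A is latently infected and receives 5 × 10⁷ pfu. Dose and population differ along with route, so even a narrow interval would not isolate the effect of route.

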13 DATA MANAGEMENT

13.1 Source Data

Source documents are where data are first recorded, and from which participants' CRF data are obtained. These include the CRF itself (history and examination), the volunteer consent form, blood and microbiology results, CT report, GP response letter, copy of bronchoscopy report and any further correspondence relating to the volunteer regarding medical/clinical issues. The CRF will be paper or electronic and paper together with electronic diary cards.

CRF entries will be considered source data if the CRF is the site of the original recording (e.g. there is no other written or electronic record of data). All documents will be stored safely in confidential conditions. On all trial-specific documents, other than the signed consent, the participant will be referred to by the trial participant number/code, not by name.

13.2 Access to Data

Direct access will be granted to authorised representatives from the Sponsor, host institution and the regulatory authorities to permit trial-related monitoring, audits and inspections. All information relating to the trial and its volunteers will be held in strict confidence, and in accordance with ICH E6 GCP and institutional requirements.

13.3 Data Recording and Record Keeping

The Chief Investigator will be responsible for collecting, recording, analysing, and storing all the data accruing from the trial. These tasks may be delegated to other Investigators. Paper CRFs will be stored in a key-locked cabinet at each site, and electronic CRFs on the OpenClinica™ database, which is stored electronically on secure servers that are outsourced by OpenClinica™. Data from paper CRFs will be transcribed onto the OpenClinica™ database. Some data may be duplicated anonymously into an electronic Microsoft Excel™ file on the CCVTM secure server for clinical monitoring through the trial.

Trial records will be held by the Investigator for as long as required by legislation as a minimum (currently until at least 2 years after the last marketing authorisation for the product or 2 years after discontinuation of clinical development of an investigational product) and in order to enable dissemination of study results after publication, and to enable decoding and destruction of anonymized samples if subsequently requested by a volunteer. Data will subsequently be transferred to a secure archive in accordance with the Data Protection Act. Volunteers will be assigned individual unique trial numbers for identification on all trial records, except where the use of identifiable information is unavoidable (including on GP correspondence, registration documents, and consent forms).

14 QUALITY ASSURANCE PROCEDURES

14.1 Quality Assurance

Investigator procedures

Approved site-specific SOPs will be used at all clinical and laboratory sites.

Modification to protocol

No substantial amendments to this protocol will be made without consultation with, and agreement of, the Sponsor. Any substantial amendments to the trial that appear necessary during the course of the trial must be discussed by the Investigator and Sponsor concurrently. If agreement is reached concerning the need for an amendment, it will be produced in writing by the CI and will be made a formal part of the protocol following ethical and regulatory approval.

An administrative change to the protocol is one that modifies administrative and logistical aspects of a protocol but does not affect the volunteers' safety, the scientific value of the trial, the conduct of the study or safety of the IMP. An administrative change is a non-substantial amendment and does not require REC approval. However, the REC will be notified whenever an administrative change is made.

The Chief Investigator is responsible for ensuring that changes to an approved trial, during the period for which REC approval has already been given, are not initiated without REC review and approval except to eliminate apparent immediate hazards to the volunteer.

Protocol deviation

All deviations from the protocol will be documented in a protocol deviation form and filed in the trial master file.

14.2 Monitoring

Data will be evaluated for compliance with the protocol and accuracy in relation to source documents. The trial will be conducted in accordance with procedures identified in the protocol. Regular monitoring will be performed according to ICH GCP. According to applicable SOPs, the Monitors will verify that the clinical trial is initiated, conducted and completed, and data are generated, documented and reported in compliance with the protocol, GCP and the applicable regulatory requirements.

15 SERIOUS BREACHES

The Medicines for Human Use (Clinical Trials) Regulations contain a requirement for the notification of "serious breaches" to the MHRA within 7 days of the Sponsor becoming aware of the breach. A serious breach is defined as "A breach of GCP or the trial protocol which is likely to affect to a significant degree:

- the safety or physical or mental integrity of the volunteers of the trial
- the scientific value of the trial"

In the event that a serious breach is suspected the Sponsor must be contacted within 1 working day. In collaboration with the CI, the serious breach will be reviewed by the Sponsor and, if appropriate, the Sponsor will report it to the REC committee, Regulatory Authority and the NHS host organisation within 7 calendar days.

16 ETHICAL AND REGULATORY CONSIDERATIONS

16.1 Declaration of Helsinki

The Investigator will ensure that this trial is conducted in accordance with the principles of the Declaration of Helsinki as agreed by the World Medical Association General Assembly (Washington 2002).

16.2 Good Clinical Practice

The Investigator will ensure that this trial is conducted in accordance with ICH Good Clinical Practice (GCP), the requirements of the Medicines for Human Use (Clinical Trial) Regulations 2004, and local regulatory requirements.

16.3 Approvals

A copy of the protocol, proposed informed consent form, other written volunteer information and the proposed advertising material will be submitted to an independent REC for written approval. The Investigators will submit and, where necessary, obtain approval from the REC for all subsequent substantial amendments to the protocol and informed consent document. The Investigators will notify deviations from the protocol or SAEs occurring at the site to the Sponsor and will notify the REC of these in accordance with local procedures.

16.4 Reporting

The CI shall submit once a year throughout the clinical trial, or on request, an Annual Progress Report to the REC, host organisation and Sponsor. In addition, an End of Trial notification and final report will be submitted to the MHRA, the REC, host organisation and Sponsor.

16.5 Volunteer Confidentiality

The trial staff will ensure the volunteers' anonymity is maintained. All documents will be stored securely and only accessible by trial staff and authorised personnel. No information concerning the trial or the data will be released to any unauthorised third party, without prior written approval of the sponsor. The trial will comply with the Data Protection Act, which requires data to be anonymised as soon as it is practical to do so.

16.6 Expenses and Benefits

Volunteers will be compensated *pro rata* for their time, travel and for trial procedures while participating in the trial, amounting to a total of approximately £505-£625, depending on the exact number of visits, site of recruitment and whether any repeat or additional visits are necessary.

17 FINANCE AND INSURANCE

17.1 Funding

This trial will be financed by research grants from TBVI and The Wellcome Trust, held by [name].

17.2 Indemnity

If any volunteer is harmed as a result of this trial, medical care will be provided under the NHS.

Negligent Harm

Indemnity and/or compensation for negligent harm arising specifically from an accidental injury for which the University is legally liable as the Research Sponsor will be covered by the University of Oxford.

Non-Negligent Harm

Indemnity and/or compensation for harm arising specifically from an accidental injury, and occurring as a consequence of the Research volunteers' participation in the trial for which the University is the Research Sponsor will be covered by the University of Oxford.

